8. STATISTICAL METHODOLOGY AND STATISTICAL ANALYSES

8.1 Analysis Methods

All analyses will be run on the safety population with no sensitivity analyses, sub-group analyses, or covariate adjustments planned.

8.1.1 Safety Outcome Analyses

The safety outcomes will be considered in two ways: the absolute number and the person-week incidence rates (*Section 3.2*) of selected adverse events following transplantation. The person-week incidence rate will be estimated using proportions and exact binomial two-sided 95% confidence intervals for the Safety Sample as a whole and within the two analysis periods defined above. The absolute number and the estimated incidence proportions of the following will be reported:

- Biopsy-proven acute and/or chronic rejection
- Grade ≥ 3 infections as defined in Section 13.3.1 of the Protocol
- Wound complications (\geq CTCAE Grade 3)
- Anemia, neutropenia, and/or thrombocytopenia (\geq CTCAE Grade 3)
- Adverse events attributable to the darTreg infusion including infusion reaction/cytokine releaser syndrome (\geq CTCAE Grade 3), and malignant cellular transformation.

Descriptive statistics will also be presented for:

- The severity of biopsy-proven acute and/or chronic rejection
- Reasons for termination of subjects who did not receive leukapheresis
- Use of concomitant medications

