# 15.6 Sample Size Considerations

This pilot study is designed to evaluate 18 subjects through Stage 3 in a modified 3+3 dose escalation design. Therefore, no formal power and sample size analyses have been performed. However, with 18 evaluable subjects undergoing darTreg supportive IS for 12 weeks of follow-up (6 subjects for 40 weeks of follow-up) and up to 12 evaluable subjects undergoing darTreg infusions for 28 weeks of follow-up after infusion, exact 95% confidence intervals on person-week incidence rates will vary in width by analysis period. For example, the following table (*Table 8. Incidence Rates and Confidence Intervals for Selected Numbers of Events and Person-Weeks*) shows incidence rates and confidence intervals for selected numbers of events and person-weeks of 216 (18 subjects x 12 weeks), 336 (12 subjects x 28 weeks), and 384 (6 subjects x 40 weeks + 12 subjects x 12 weeks) in the two analysis periods. It is not known at this time how many subjects may be expected to comprise the entire Safety Sample, which includes subjects who only received leukapheresis.

Confidential Page 65 of 80

Table 8. Incidence Rates and Confidence Intervals for Selected Numbers of Events and Person-Weeks

Number of	Total Person-	Person-Weeks	Lower 95%	Upper 95% Confidence
Events	Weeks	Incidence Rate	Confidence Limit	Limit
2	216	0.0093	0.0011	0.0334
4	216	0.0185	0.0050	0.0474
6	216	0.0278	0.0102	0.0605
8	216	0.0370	0.0160	0.0730
10	216	0.0463	0.0222	0.0851
12	216	0.0556	0.0287	0.0970
14	216	0.0648	0.0354	0.1087
16	216	0.0741	0.0423	0.1203
18	216	0.0833	0.0494	0.1317
20	216	0.0926	0.0566	0.1430
2	336	0.0060	0.0007	0.0215
4	336	0.0119	0.0032	0.0305
6	336	0.0179	0.0066	0.0389
8	336	0.0238	0.0103	0.0469
10	336	0.0298	0.0143	0.0547
12	336	0.0357	0.0185	0.0624
14	336	0.0417	0.0228	0.0699
16	336	0.0476	0.0272	0.0773
18	336	0.0536	0.0317	0.0847
20	336	0.0595	0.0364	0.0919
2	384	0.0052	0.0006	0.0188
4	384	0.0104	0.0028	0.0267
6	384	0.0156	0.0057	0.0340
8	384	0.0208	0.0090	0.0410
10	384	0.0260	0.0125	0.0479
12	384	0.0313	0.0161	0.0546
14	384	0.0365	0.0199	0.0612
16	384	0.0417	0.0238	0.0677
18	384	0.0469	0.0278	0.0741
20	384	0.0521	0.0318	0.0804

Confidential Page 66 of 80

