2.2 Safety Objective

This study will evaluate the safety, tolerability, and dose limiting toxicities (DLT's) of a Treg-supportive IS regimen and darTreg infusion for adult, de novo, liver transplant recipients.

3. Sample Size Considerations

This pilot study is designed to evaluate 18 subjects through Stage 3 in a modified 3+3 dose escalation design. Therefore, no formal power and sample size analysis have been performed. However, with 18 evaluable subjects undergoing darTreg supportive IS for 12 weeks of follow-up (6 subjects for 40 weeks of follow-up) and up to 12 evaluable subjects undergoing darTreg infusions for 28 weeks of follow-up, exact 95% confidence intervals on person-week incidence rates will vary in width by analysis period. For example, the following table (**Table 1**) shows incidence rates and confidence intervals for selected numbers of events and person-weeks of 216 (18 subjects x 12 weeks), 336 (12 subjects x 28 weeks), and 384 (6 subjects X 40 weeks and 12 subjects X 12 weeks) in the two analysis periods. It is not known at this time how many subjects may be expected to comprise the entire Safety Sample.

Table 1. Incidence Rates and Confidence Intervals for Selected Numbers of Events and Person-Weeks

Number of Events	Total Person-Weeks	Person-Weeks Incidence Rate	Lower 95% Confidence Limit	Upper 95% Confidence Limit
2	216	0.0093	0.0011	0.0334
4	216	0.0185	0.0050	0.0474
6	216	0.0278	0.0102	0.0605
8	216	0.0370	0.0160	0.0730
10	216	0.0463	0.0222	0.0851
12	216	0.0556	0.0287	0.0970
14	216	0.0648	0.0354	0.1087
16	216	0.0741	0.0423	0.1203
18	216	0.0833	0.0494	0.1317
20	216	0.0926	0.0566	0.1430
2	336	0.0060	0.0007	0.0215
4	336	0.0119	0.0032	0.0305
6	336	0.0179	0.0066	0.0389
8	336	0.0238	0.0103	0.0469

10	336	0.0298	0.0143	0.0547
12	336	0.0357	0.0185	0.0624
14	336	0.0417	0.0228	0.0699
16	336	0.0476	0.0272	0.0773
18	336	0.0536	0.0317	0.0847
20	336	0.0595	0.0364	0.0919
<hr/>				
2	384	0.0052	0.0006	0.0188
4	384	0.0104	0.0028	0.0267
6	384	0.0156	0.0057	0.0340
8	384	0.0208	0.0090	0.0410
10	384	0.0260	0.0125	0.0479
12	384	0.0313	0.0161	0.0546
14	384	0.0365	0.0199	0.0612
16	384	0.0417	0.0238	0.0677
18	384	0.0469	0.0278	0.0741
20	384	0.0521	0.0318	0.0804

4. General analysis and reporting conventions

The following analyses and reporting conventions will be used:

- Categorical variables will be summarized using counts (n) and percentages (%) and will be presented in the form n (%). Percentages will be rounded to one decimal place.

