5. ANALYSIS SAMPLES

The Safety Sample will be comprised of all study subjects who are consented and receive any study therapy, including leukapheresis, Treg-supportive IS and darTreg infusion. This excludes consented subjects who were terminated before receiving any study treatment.

Safety and clinical outcomes will be analyzed within the Safety Sample as a whole and within the following two treatment-related analysis periods during which:

- Subjects receive any darTreg supportive IS
- Subjects receive darTreg infusions at any dose.

Subjects will contribute adverse events and weeks at risk to each analysis period for as long as they are on the corresponding study treatment in that analysis period. Thus, if they progress from darTreg supportive IS to darTreg infusions at any dose, they will contribute subsequent adverse events and weeks at risk to the darTreg infusion analysis period when they initiate any darTreg infusion and that will continue until the end of their follow-up time on study.

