9.2 Adverse Events

All adverse events will be classified by system organ class and preferred term, according to a standardized thesaurus (MedDRA version 17.0). The severity of AEs will be classified using the National Cancer Institute's Common Toxicity Criteria for Adverse Events, with the exception of infections which will be graded according to protocol definitions.

An overall summary table will be developed to report the number of events and the number and percentage of subjects having at least one event in the following categories:

- AEs
- AEs indicated as serious (SAEs)
- AEs that lead to study discontinuation
- AEs with an outcome of death
- AEs reported by maximum severity

In addition, adverse events classified by MedDRA system organ class and preferred term will be summarized for each study cohort and overall for each of the following:

- All AEs
- AEs by maximum severity
- AEs by study stage

The summary tables will present the total number of events as well as the number and percentage of subjects experiencing the events. When reporting the number of AEs, if the same AE occurs for a subject on multiple occasions the event will be counted once for each occurrence. When reporting the number of subjects experiencing the events, a subject will only be counted once if they ever experience an event within the particular system organ class or preferred term. Percentages will be based on the number of subjects in the analysis population.

A summary table of incidence rates adverse events classified by system organ class and MedDRA preferred term will be provided. Incidence rate for a system organ class or preferred term will be defined as the number of adverse events divided by the person-time since the subject enrolled.

Separate data listings will be provided for AEs leading to study discontinuation.

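### SAP 8.1.1 does not say what counts as an event, and the implied exact interval on total events can be too narrow for outcomes that recur in the same subject

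*SAP*

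**What the plan says.** SAP 8.1.1 opens with "The safety outcomes will be considered in two ways: the absolute number and the person-week incidence rates". It continues: "The person-week incidence rate will be estimated using proportions and exact binomial two-sided 95% confidence intervals". It then introduces the five outcomes with "The absolute number and the estimated incidence proportions of the following will be reported". Protocol 15.4.2 likewise calls the safety outcomes person-week rates with exact two-sided 95% intervals. Neither section says whether a subject with three events adds one or three.

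The counting rule has to be pieced together from other places:

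- SAP 5 (and protocol 15.4.1): "Subjects will contribute adverse events and weeks at risk to each analysis period for as long as they are on the corresponding study treatment". Time at risk is not cut at a first event.
- SAP 9.2, on numbers of AEs: "if the same AE occurs for a subject on multiple occasions the event will be counted once for each occurrence".
- SAP 9.2, on rates: "Incidence rate for a system organ class or preferred term will be defined as the number of adverse events divided by the person-time".
- SAP section 3, Table 1 (identical to protocol Table 8): limits for 2 to 20 events in 216, 336 or 384 person-weeks. The first two are built on designs such as "with 18 evaluable subjects undergoing darTreg supportive IS for 12 weeks of follow-up" and "up to 12 evaluable subjects undergoing darTreg infusions for 28 weeks of follow-up after infusion".

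SAP 9.2 also counts subjects once per system organ class or preferred term, and SAP 9.3 adds displays for infection, severe rejection and chronic rejection. No interval is attached to any of these subject counts. SAP 8.1 plans no sensitivity analysis.

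**The concern.** An exact interval on a total count uses only the total and the exposure. It cannot tell 12 events in 12 subjects from 12 events in 4 subjects, although these are very different safety pictures. It is valid when events are independent and subjects share one rate. That is doubtful here, most clearly for outcome 4.

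- Protocol 14.3.1 records neutrophil, hemoglobin and platelet decreases as separate AEs, and the outcome pools them.
- Under the treatment-emergent rule in the same section, a fall after recovery is a new event in the same patient.
- Protocol 5.2 notes that liver transplant patients start with depressed leukocyte and platelet counts.

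Protocol 15.4 makes these intervals the stated analysis of the safety outcomes. If a few subjects supply most of the events, the interval overstates how much 12 or 18 people can tell us.

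**Working it through.** **1. Reproduce the plan's table.** With x events in T person-weeks, the exact Poisson limits are χ²(0.025; 2x)/(2T) and χ²(0.975; 2x+2)/(2T).

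- x = 12, T = 12 × 28 = 336: 6.20/336 = 0.0185 and 20.96/336 = 0.0624, as printed.
- x = 20, T = 336: 12.22/336 = 0.0364 and 30.89/336 = 0.0919, as printed.

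All 30 rows reproduce this way. The exact binomial limits named in SAP 8.1.1, with person-weeks as trials, reproduce none (12/336 gives 0.0186 to 0.0616). That mismatch is a separate matter: coverage in step 4 is the same to three decimals with either method.

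**2. Do the documents imply repeats?** Twenty events in 12 subjects is 20/12 = 1.7 per subject, which is impossible if each subject counts once. With time at risk running on after an event and a rate defined as AEs over person-time, total events over total person-weeks is the natural reading.

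**3. One worked case.** Take 12 events in 12 subjects × 28 weeks, as three events in each of four subjects.

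- Mean per subject 1; sample variance (4 × 2² + 8 × 1²)/11 = 24/11 = 2.18; dispersion 2.18.
- Planned interval: 0.0185 to 0.0624.
- Between-subject variance: SE of the log rate = √(2.18/12) = 0.426. With t on 11 df (2.201), 0.0357 × exp(±0.938) = 0.0140 to 0.0913. With z it is 0.0155 to 0.0824.
- On the log scale the t interval is 1.88/1.22 = 1.5 times as wide as the planned one.
- Subject level: 4/12 = 33%, exact binomial 9.9% to 65.1%.

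**4. Coverage under clustering.** Assumption, not in the documents: subject rates follow a gamma distribution with mean 1 and variance v, and exposure is equal. The total over n subjects with expected count μ then has variance μ(1 + μv/n). For μ = 20, n = 12, v = 1 this is 20 × (1 + 20/12) = 53.3, or 2.7 times Poisson. Coverage (%) of the nominal 95% exact Poisson interval with 12 subjects:

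| Expected events | v = 0 | v = 0.5 | v = 1 | v = 2 |
|---|---|---|---|---|
| 1 | 98 | 97.8 | 97.6 | 97.1 |
| 2 | 98 | 97.9 | 97.4 | 96.6 |
| 3 | 99 | 98.3 | 97.7 | 96.5 |
| 4 | 96 | 94 | 93 | 90 |
| 10 | 97 | 94 | 91 | 84 |
| 20 | 96 | 87 | 79 | 67 |

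With 18 subjects × 12 weeks and 12 expected events, coverage is 92%, 89% and 82% for v = 0.5, 1 and 2.

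**5. Multi-lineage cytopenia.** Also assumed: an episode yields 1, 2 or 3 events with probability 0.5, 0.3 and 0.2, and lineages are counted separately. The variance relative to Poisson is (0.5×1 + 0.3×4 + 0.2×9)/(0.5 + 0.6 + 0.6) = 3.5/1.7 = 2.1. Coverage is 88% at 10 expected events and 84% at 20.

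**6. Does a subject-level interval hold up?** For the proportion of subjects with at least one event, exact binomial limits kept at least 95.5% coverage in every simulated setting (12 or 18 subjects, 4 to 20 expected events, v from 0 to 4).

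**The case against.** The strongest reply is that nothing in SAP 8.1.1 says repeats are counted. The each-occurrence sentence sits in SAP 9.2 and governs the general AE tables, 8.1.1 itself speaks of incidence proportions, and Table 1 is offered as an example rather than a forecast. That stands as far as it goes. A reader might infer that the SAP expressly counts every repeat for the five outcomes; it does not. The documented gap is an unstated counting unit, with repeats as the best-supported reading.

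Second, high counts are unlikely for several outcomes. One grade ≥3 infection or one chronic rejection triggers a hold for DSMB review, as does one severe acute rejection after infusion (protocol 14.8.1, Table 7). Protocol 1.2.3 cites 2.9% to 7.0% treated biopsy-proven rejection at one year, which is 12 × 0.029 = 0.3 to 18 × 0.07 = 1.3 subjects, although protocol biopsies may find more. Outcome 5 follows a single infusion. This stands, and it limits the concern mainly to cytopenia, wound complications and non-severe rejection. Table 7 has no row for any of these.

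Third, the analyses are labelled descriptive, and holds rest on event counts, not on these intervals. A reader might infer that decisions turn on them; the documents do not support that. The intervals are nevertheless the planned statement of precision for the safety outcomes.

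Fourth, subject counts and listings already let a reader see clustering. That is partly so, but they carry no interval, and no subject count is specified for the pooled cytopenia outcome.

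Fifth, a simple proportion of subjects ignores unequal exposure: 40 weeks for 6 subjects and about 12 for the others in the supportive-IS period. This is correct, and it is why the fix pairs the proportion with a first-event rate.

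**Conclusion.** The point holds in a limited form. The plan leaves the counting unit open. On its most natural reading, it puts an independence-based interval on total events.

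Under-coverage depends on the event count and on an assumed degree of clustering. With gamma variance 0.5 to 2 and 12 subjects, coverage is about 94% to 90% at 4 expected events, 94% to 84% at 10 and 87% to 67% at 20. With no clustering the interval is slightly conservative.

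A reader might infer that all five intervals are too narrow; they are not. At 3 or fewer expected events, between-subject clustering leaves coverage above 96%. Nor do the documents establish that one marrow-suppression episode will count as three events, because the pooled wording also allows one composite event. That ambiguity is itself a reason to state the rule. The change is worth making before analysis, chiefly for outcome 4.

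**What to change.** In SAP 8.1.1 and protocol 15.4.2, state the counting unit for each outcome. For outcomes 1 to 4, within each analysis period:

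- report subjects with at least one event over subjects at risk, with exact binomial 95% limits;
- because exposure is unequal, also report first events over person-weeks to first event, with exact Poisson 95% limits;
- count a subject once for the pooled cytopenia outcome, and show anemia, neutropenia and thrombocytopenia separately;
- keep total event counts and rates to show the burden of recurrence, either without an interval or with one based on between-subject (robust) variance.

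The cost is revised wording, a time-to-first-event derivation and somewhat wider intervals. No new data are needed.

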#### 15.4.2 Analysis of Safety Outcomes

As the safety outcomes are all person-week incidence rates of selected AEs as described in *Section 3.2*, they will be estimated using proportions and exact two-sided 95% confidence intervals in the Safety Sample as a whole and within the two analysis periods defined above.

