2.1 Safety Outcomes

The safety, tolerability, and dose limiting toxicities of darTreg therapy given within the context of a Treg supportive IS regimen will be evaluated with the rate of the following events within 40 weeks of transplantation:

Clinical outcomes that will be described are:

1. Incidence and severity of biopsy-proven acute and/or chronic rejection
2. Incidence of \geq Grade 3 infections as defined in Section 13.3.1
3. Incidence of wound complications (\geq CTCAE Grade 3)
4. Incidence of anemia, neutropenia, and/or thrombocytopenia (\geq CTCAE Grade 3)
5. Incidence of adverse events attributable to the darTreg infusion including infusion reaction/cytokine releaser syndrome (\geq CTCAE Grade 3), and malignant cellular transformation.

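### SAP 8.1.1 names exact binomial limits and incidence proportions for a person-week rate, but the plan's own table holds exact Poisson limits; the SAP 9.2 rate table also counts time without routine AE collection

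*SAP*

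**What the plan says.** SAP 8.1.1 sets the method for the five safety outcomes: "The person-week incidence rate will be estimated using proportions and exact binomial two-sided 95% confidence intervals". This applies to the full Safety Sample and to each of its two treatment-related periods. The next sentence names what will be shown: "The absolute number and the estimated incidence proportions of the following will be reported". Protocol 15.4.2 describes the outcomes as person-week incidence rates and says that "they will be estimated using proportions and exact two-sided 95% confidence intervals". It does not name a distribution.

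The denominator is person-time. SAP section 5 states: "Subjects will contribute adverse events and weeks at risk to each analysis period". SAP section 3 introduces Table 1 by saying that "exact 95% confidence intervals on person-week incidence rates will vary in width by analysis period". Table 1 repeats protocol Table 8 and has 30 rows: 2 to 20 events in steps of two, over 216, 336 and 384 person-weeks.

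On the time window, SAP 2.1 says that safety is "evaluated with the rate of the following events within 40 weeks of transplantation", and 8.1.1 refers to events following transplantation. SAP 9.2 has a separate rate table by system organ class and preferred term. Its rate is "defined as the number of adverse events divided by the person-time since the subject enrolled".

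Protocol 14.4.1 limits AE collection in Stage 1 to the period from the PBMC collection procedure until 72 hours after it, plus later events that the investigator links to that procedure. Collection resumes with the first Thymoglobulin dose.

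**The concern.** A person-week is not a Bernoulli trial. One subject supplies many of them, events can recur, and the choice of a week as the unit is arbitrary. Exact binomial limits belong to a count of subjects out of subjects, and so does the term incidence proportion in normal usage. If the plan's table was built with Poisson limits, 8.1.1 instructs the analyst to use a method that cannot reproduce it. The five safety outcomes would then be reported with intervals and a label that do not match the quantity.

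The 9.2 rate table raises a different problem. Time from enrollment to the first Thymoglobulin dose enters the denominator, but almost no AEs can enter the numerator during that time. In a safety trial, that error makes rates look lower than they are.

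**Working it through.** **Inputs.** Events x and person-weeks T are from SAP Table 1. T is 216 = 18 × 12, 336 = 12 × 28, and 384 = 6 × 40 + 12 × 12. The level is two-sided 95%.

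**Formulas.**
- Exact Poisson: lower = χ²(0.025; 2x) / 2T; upper = χ²(0.975; 2x + 2) / 2T.
- Exact binomial (Clopper-Pearson), person-weeks as trials: lower = Beta(0.025; x, T − x + 1); upper = Beta(0.975; x + 1, T − x).

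**Reproducing the table, worked row (20 events, 216 person-weeks).** The rate is 20/216 = 0.0926. Poisson lower = 24.433/432 = 0.0566 and upper = 61.777/432 = 0.1430. The table prints 0.0566 and 0.1430. The binomial limits are 0.0575 and 0.1394.

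| Events / person-weeks | Table | Exact Poisson | Exact binomial | Width, binomial ÷ Poisson |
|---|---|---|---|---|
| 20 / 216 | 0.0566–0.1430 | 0.0566–0.1430 | 0.0575–0.1394 | 0.947 |
| 10 / 336 | 0.0143–0.0547 | 0.0143–0.0547 | 0.0144–0.0541 | 0.981 |
| 6 / 336 | 0.0066–0.0389 | 0.0066–0.0389 | 0.0066–0.0385 | 0.987 |
| 2 / 384 | 0.0006–0.0188 | 0.0006–0.0188 | 0.0006–0.0187 | 0.993 |

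**All 30 rows, at four decimals.** Poisson agrees in 30 of 30. Binomial agrees in 0 of 30 (7 lower limits, no upper limit). The width ratio runs from 0.9474 (20/216) to 0.9930 (2/384), so binomial intervals are 5.3% to 0.7% narrower. Upper limits differ by 0.0036 (0.1430 − 0.1394) in the first of these rows and by 0.0001 in the second. For rows with 2 to 6 events the intervals are 0.7% to 2.1% narrower, and the upper limits are 0.0001 to 0.0010 lower.

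**Dependence on the time unit.** For 20 events in 216 weeks, expressed per week, the binomial limits are:
- weeks as trials (216): 0.0575 to 0.1394
- days as trials (1,512): 0.0567 to 0.1425
- four-week blocks as trials (54): 0.0607 to 0.1281

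The Poisson limits do not change with the unit.

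**The 9.2 denominator.** Let C be person-time with AE collection from the first Thymoglobulin dose, and W the time between enrollment and that dose. Leaving aside the few events around PBMC collection, the 9.2 rate equals the rate over C multiplied by C/(C + W). Cohort 1 has no PBMC collection visit (Appendix 1, first footnote), so all of W is uncollected for those subjects. For Cohorts 2 to 4, W is covered only during PBMC collection and the 72 hours after it. Neither document gives W. The six-month entry for Screen A in the visit-window table is a screening window, not a waiting time. The direction of the dilution is therefore known, but its size is not.

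**The case against.** The strongest reply is that this is a matter of wording. Table 1 is introduced only as an example under sample size. At the event counts likely in so small a trial the limits barely move. The analyses are descriptive (protocol 15.4), and the stopping rule in protocol Table 7 uses absolute counts. All of that stands and sets the severity. It does not remove the contradiction between the named method and the table.

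Three stronger readings are tempting, but the documents do not support them.

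- *The five safety outcomes are themselves diluted by waiting-list time.* The since-enrollment definition in 9.2 is written for the system organ class and preferred term table. SAP 2.1 and 8.1.1 tie the five outcomes to transplantation, and the planning person-weeks also run from there. What stays open is narrower. SAP section 5 defines weeks at risk only within the two treatment periods, while the whole Safety Sample includes subjects with leukapheresis only, who have no transplantation start.
- *8.1.1 will report per-subject proportions.* The label allows that reading, and the two quantities differ. Two events in 216 person-weeks are 0.0093 per week. If they fell in two of 18 subjects (an assumption), the proportion is 2/18 = 11.1% (exact binomial 1.4% to 34.7%). But the sentence just before the label says that the person-week rate is estimated using proportions, so per person-week is the more natural reading.
- *The handling of repeat events is undefined.* SAP section 5 lets subjects contribute events and time for as long as they are on treatment, without a cut at the first event. SAP 9.2 says, for the number of AEs, that "if the same AE occurs for a subject on multiple occasions the event will be counted once for each occurrence". Together these largely answer the question.

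A further fair objection concerns the remedy. If all person-time simply started at transplantation or at the first Thymoglobulin dose, collected PBMC-procedure events would fall before time zero, and subjects who are transplanted but never receive Thymoglobulin would have no place. The fix must cover both.

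**Conclusion.** SAP 8.1.1 is wrong as written. It prescribes binomial limits, and a label that suggests a proportion, for an event rate over person-time. The plan's own exact limits are Poisson in every row. The consequence is intervals 0.7% to 5.3% narrower than the table and upper limits 0.0001 to 0.0036 lower, taking person-weeks as the binomial trials. Table 1 and Table 8 are arithmetically correct, and no trial decision depends on the difference.

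Secondarily, the 9.2 rate table uses a denominator that does not match the AE collection period. This biases those rates downward by an unknown amount. The finding rests on protocol 14.4.1 as the rule for AE collection. Severity is low: a specification error that is worth correcting before analysis because it is cheap to correct.

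**What to change.** 1. **SAP 8.1.1.** Replace the reference to proportions and exact binomial limits with *events per person-week with exact Poisson two-sided 95% confidence intervals*. Replace incidence proportions with *person-week incidence rates*.
2. **Protocol 15.4.2.** Replace proportions with *events per person-week*.
3. **SAP 9.2, and the whole-sample rate in 8.1.1.** Count only person-time during which AEs are collected, that is, from the first Thymoglobulin dose onward. That dose is due within 72 hours of transplantation, so against a transplantation start each subject followed for 40 weeks loses at most 3 of 280 days, or 1.1%.
4. **Stage 1 events.** Report events from the PBMC-collection window separately, as counts over all subjects with PBMC collection. Protocol 15.4.1 already defines this third subset; SAP section 5 omits it and should carry it.
5. **Safety Sample members who never receive Thymoglobulin.** Show them as counts only, whether or not they were transplanted.
6. **Optional.** For the five outcomes, add subjects with at least one event over subjects at risk, with a Clopper-Pearson interval, and reserve the terms proportion and exact binomial for that column. SAP 9.2 and 9.3 already plan subject counts and percentages for AEs and SAEs, so this adds mainly the interval.

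The cost is a few sentences in the SAP, one phrase in the protocol and, if item 6 is taken up, one column per table. Tables 1 and 8 stay as they are.
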